6.4. Baseline and Other Summaries and Analyses

Descriptive summary including N, mean, SD, median, minimum, and maximum will be presented for continuous baseline variables. Frequency and percentage will be provided for categorical baseline variables.

6.4.1. Baseline Summaries

The summaries will be provided for demographic data collected at the entry of the OLE period, if data permits.

6.4.2. Study Conduct and Participant Disposition

Frequency counts and percentage will be reported for participant discontinuation due to adverse events and reasons for discontinuation, completion of each OLE year, number of subjects assessed, and number of subjects achieved final height.

Data will be reported in accordance with the Pfizer reporting standards.

6.4.3. Study Treatment Exposure

Frequency counts and percentage will be reported for 6-month intervals for treatment duration in main period and OLE phase. The patient year will be descriptively summarized (median, mean and SD) in main period and OLE.

6.4.4. Concomitant Medications and Nondrug Treatments

The concomitant medication(s) and non-drug treatment(s) in OLE period will be provided in the listings.

6.5. Safety Summaries and Analyses

All the safety data will be summarized descriptively through the appropriate data tabulations in safety population (defined in [Section 4](#)) according to Pfizer Safety Rulebook and CDISC standards analyses, to evaluate any potential risk associated with the safety and toleration of administering somatogon pediatric GHD patients.

6.5.1. Adverse Events

TEAE will be summarized with counts and percentage for safety population (defined in [Section 4](#)). The number and percentage of subjects who experienced at least one TEAE as well as the number and percentage of subjects who experienced each specific system organ class (SOC) and preferred term (PT) will be summarized and sorted by descending order of overall incidence.

All AEs will be reported in a data listing.

For analysis purposes, all AEs will be classified to the appropriate MedDRA PT and SOC. For each subject, multiple events that map to the same PT will only be counted once for the PT, and multiple PTs within an SOC will only be counted once for that SOC to assess patient incidence of events by PT and SOC. The count and percentage of patients with each PT and SOC will be summarized for each treatment group. Relationship and severity of AEs will be summarized (count and % of patients, incidence rate based on person-year) for each treatment group. For these summaries, multiple occurrences of an event within a patient will be classified as a single observation with the strongest relationship and maximum severity ratings. In addition, frequency tables of all reported events with each associated relationship and severity will be presented. Serious adverse events (SAEs) will be classified by the investigator and will be summarized by treatment group, PT and SOC, as well as total patients exposed.

In addition to the SOC and PT defined in the live MedDRA version at the final reporting stage, the adverse event of special interest (AESI) will be also summarized using frequency and percentage.

6.5.2. Laboratory Data

Laboratory data will be descriptively summarized by each clinical laboratory panel of hematology, chemistry, lipid profile, glucose metabolism, endocrinology, urinalysis. Shift tables will also be provided for each panel to present the count and percentage shifts from baseline among the categories of low, normal, and high.

6.5.3. Vital Signs

All vital sign data will be listed by participant and visit.

Though vital signs will be collected during each site visit per standard of care, only vital sign collected at the baseline, Month 3, 6, 9 and 12 in each of the OLE year will be summarized descriptively. Absolute values, change from baseline, and percent change from baseline for vital sign data will be summarized using N, mean, SD, median and range.

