### 5.3 LT-OLE PERIOD (VISITS 10 TO 16)

After completion of 12 months treatment in the main study and continuing to meet the LT-OLE inclusion/exclusion criteria of this protocol, patients will be eligible to rollover into a single arm LT-OLE treatment period with MOD-4023. An informed consent/assent will be obtained from patients and/or parent/s or legal/authorized guardian as required per local regulation.

Patients who received MOD-4023 during the main study will continue with the same dose of MOD-4023 (mg/kg/wk), adjusted for body weight. For these patients, study visits will take place every three months on Day 4 (-1) post-dose. These patients will consent to the LT-OLE preferably during Visit 7 of the main study to ensure availability of MOD-4023 at their next visit. If necessary, informed consent can be obtained at Visit 8 main study/10 LT-OLE. These Patients will continue treatment at Visit 8/10, skip Visits 9 and 11 and have a telephone visit at Visit 12 (one month post LT-OLE entry (Month 13 [ $\pm 2$ wk])).

Patients who received Genotropin®, during the main study will be switched to MOD-4023 starting no less than one day [ $+2$ wk] after cessation of Genotropin® treatment. Recommended injection days are indicated in Appendix E. These patients will consent to the LT-OLE preferably during Visit 7 of the main study to ensure availability of MOD-4023 at their next visit. If necessary, informed consent can be obtained at Visit 8/10. Patients will begin treatment with MOD-4023 at Visit 8/10, skip Visit 9 and have additional onsite visits at Visit 11 (Month 12, Day 10 post first MOD-4023 dose [ $10+4$  days]) and Visit 12 (one month (Month 13 post first MOD-4023 dose [ $\pm 2$ wk])). All Patients will be provided with a diary card.

For all patients switching from Genotropin® to MOD-4023, the following will also be done:

- MOD-4023 will be dispensed based on patient weight at a starting dose of 0.66 mg/kg/wk.
- Training on and administration of MOD-4023 using the device.
- Local tolerability after first dose administered at site.

Patients who experience a delay for any reason between completion of the main study and entry into the LT-OLE may have to temporarily stop treatment. If initiation/re-initiation of treatment occurs less than 90 days after Visit 8 only training on and administration of MOD-4023 and local tolerability after first dose administered at site is required.

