Patients who are off treatment for more than 90 days due to technical reasons e.g. delay in approval of Protocol Amendment may be allowed to continue into the LT-OLE after confirmation of availability of all required baseline LT-OLE assessments (Visit 8/10). The following tests and assessments must be repeated:

- Safety laboratory tests: chemistry, hematology and urinalysis.
- Parameters of glucose metabolism: overnight fasting glucose, overnight fasting insulin, HbA1c.
- Assessment of anti-MOD-4023 Ab for all patients (Genotropin® group – baseline for future tests).
- Assessment of biochemical markers: IGF-1, IGF-1 SDS, IGF-BP-3 and IGF binding protein-3 (IGFBP-3) SDS serum levels.

5.3.1 Visit 11 (Month 12, Day 10 [+4days] post first MOD-4023 dose) for patients switching from Genotropin® to MOD-4023 only

The following assessments will be conducted at the study site or at the patient's home (if allowed according to local regulations):

- MOD-4023 serum levels.
- Anti-MOD-4023 Abs.
- AEs and local tolerability (aligned with Appendix H) assessment.
- Concomitant medication recording aligned with the questionnaire in [Appendix I](#).

5.3.2 Visit 12 (one month post first MOD-4023 dose(Month 13 [ $\pm 2$ wk])) will be performed on site for patients switching from Genotropin® to MOD-4023

The following assessments will be conducted at Visit 12 on Day 4 (-1) post dose:

- AEs, local tolerability, and concomitant medications.
- Overall health status assessment, including complete physical examination and vital signs.
- Urine pregnancy test once a female patient reports first menstrual cycle (menarche).
- Safety laboratory tests: chemistry, hematology and urinalysis.
- Assessment of biochemical markers: IGF-1, IGF-1 SDS, IGFBP-3 and IGFBP-3 SDS serum levels.
- Fundoscopy (ONLY if there are signs or symptoms indicative of benign intracranial hypertension).
- MOD-4023 serum levels.
- Anti-MOD-4023 Abs.
- Fundoscopy (ONLY if there are signs or symptoms indicative of benign intracranial hypertension).
- Return of used and unused injection devices to the site and diary card.
- Drug dispensing and accountability.

Existing MOD-4023 patients will have a telephone visit at Visit 12 (one month post LT-OLE entry [Month 13  $\pm 2$ wk]) to ask about AEs, local tolerability and concomitant medications. This visit will be completed using the questionnaire in Appendix I.

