#### **5.4 LT-OLE (VISITS 17 TO STUDY CLOSURE)**

Following completion of the first year of LT-OLE the following assessments will be conducted every three months on day 4 (-1) post-dose for all patients:

- Auxology measurements: Actual height (average of 3 consecutive measurements) measured on a calibrated wall mounted stadiometer.
- Overall health status assessment, including complete physical examination and vital signs assessment.
- Individual dose adjustment based on weight.

Effective Date: Date of final electronic approval

- AEs, local tolerability, and concomitant medications.
- Urine pregnancy test at every visit once a female reports first menstrual cycle (menarche).
- Fundoscopy (if there are signs or symptoms indicative of benign intracranial hypertension).
- Return of used and unused injection devices to the site and diary card.
- Drug dispensing and accountability.

The following assessments will also be conducted every six months on day 4 (-1) post-dose visits:

- Assessment of biochemical markers: IGF-1, IGF-1 SDS, IGFBP-3 and IGFBP-3 SDS serum levels.
- Safety laboratory tests: chemistry, hematology and urinalysis.
- Assessment of thyroid function: TSH, FT4.
- Parameters of glucose metabolism: overnight fasting glucose, overnight fasting insulin, HbA1c.
- Parameters of lipid metabolism: overnight fasting cholesterol, triglycerides, HDL, LDL, Lp(a), FFA.
- Assessment of MOD-4023 serum levels.
- Assessment of anti-MOD-4023 Ab.

Additional assessments will be performed once a year, every 12 months on dosing day or Day 4(-1):

- ECG.
- Bone age.
- Pubertal status (according to Tanner stages).
- For males that are 13 years and older: LH, FSH and testosterone. For females that are 12 years and older: LH, FSH and estradiol.

The following assessments will be conducted during the EOS/ET visit:

- Auxology measurements- Actual Ht (mean of 3 consecutive measurements) measured on a calibrated wall mounted stadiometer.
- AEs, local tolerability, and concomitant medications.
- Overall health status assessment, including complete physical examination and vital sign assessments.
- Safety laboratory (chemistry, hematology and urinalysis).
- Pubertal status.
- Urine pregnancy test for female patients who have reported menarche.
- Thyroid function and biochemical markers: TSH, FT4, IGF-1, IGF-1 SDS, IGFBP-3 and IGFBP-3 SDS serum levels.
- Parameters of glucose metabolism (overnight fasting glucose, overnight fasting insulin, HbA1c).

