3.5.3. Vital Signs

Vital sign data will be collected according to the Schedule of Activities in the protocol, including systolic blood pressure, diastolic blood pressure, heart rate, respiratory rate, temperature. Any clinically significant (CS) findings will be reported as an AE.

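### SAP 6.5.3 tabulates extension vital signs at fewer visits than protocol 8.6.9 asks for, names no baseline for them, and makes no allowance for age or growth

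*SAP*

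**What the plan says.** The SAP collects five vital signs in the extension, "including systolic blood pressure, diastolic blood pressure, heart rate, respiratory rate, temperature" (SAP 3.5.3). SAP 6.5.3 then does three things:

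- It lists everything: "All vital sign data will be listed by participant and visit".
- It limits the tables: "only vital sign collected at the baseline, Month 3, 6, 9 and 12 in each of the OLE year will be summarized descriptively".
- It names the statistics: "Absolute values, change from baseline, and percent change from baseline for vital sign data will be summarized", using N, mean, SD, median and range.

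SAP 3.5.3 adds a second route for individual findings: "Any clinically significant (CS) findings will be reported as an AE".

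The protocol schedules vital signs at two kinds of extension visit that are not on the SAP's list. Section 5.3.2 includes them at Visit 12, one month after the switch from Genotropin: "Overall health status assessment, including complete physical examination and vital signs". Section 5.4 includes them at the EOS/ET visit: "Overall health status assessment, including complete physical examination and vital sign assessments". Vital signs are a listed LT-OLE safety endpoint (protocol 8.4.6). Protocol 8.6.9 wants them described at every scheduled visit, with raw change, and wants abnormal results tabulated visit by visit for each treatment group.

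**The concern.** There are three linked gaps.

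**Time points.** The word *only* in SAP 6.5.3 shuts Visit 12 out of the tables and leaves the EOS/ET visit with no row of its own. Visit 12 is the first vital-sign check after switchers start somatrogon. The EOS/ET visit gives the last reading in a child who stops early. The SAP states no counterpart to the protocol's abnormal-results table.

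**Interpretation.** Entrants are boys aged 3 to 11 and girls aged 3 to 10, and the SAP's windows run to OLE Year 4. After the main study "patients will be eligible to rollover into a single arm LT-OLE treatment period with MOD-4023", so no concurrent control removes the effect of getting older. If blood pressure and heart rate move with age and size, raw and percent change combine that movement with any drug effect. A real rise in pressure could pass for growth, and a rise in heart rate could be offset by an age-related fall. The SAP uses standardised scores for height, IGF-1 and IGFBP-3, and low/normal/high shift tables for laboratory data. It states neither for vital signs.

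**Baseline.** SAP 3.4 fixes the baseline for efficacy and biomarkers but not for vital signs. Change could therefore start at main-study entry or at extension entry, about one year apart.

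**Working it through.** The plan gives no figure on this point, so there is none to reproduce. The check is a visit count, a comparison of planned outputs, and an illustration on stated assumptions.

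**Step 1: visits with vital signs against visits tabulated** (protocol 5.3.2, 5.3.3, 5.4 and Appendix A; SAP 6.5.3). OLE Months 3, 6, 9 and 12 correspond to Visits 13, 14, 15 and 16.

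| Group and period | Scheduled post-baseline visits with vital signs | Tabulated |
|---|---|---|
| Switchers, OLE Year 1 | 12, 13, 14, 15, 16 (5) | 4 of 5; 1/5 = 20% left out |
| Already on somatrogon, OLE Year 1 | 13, 14, 15, 16 (4); Visit 12 is by telephone | 4 of 4 |
| All, Year 2 onward | 4 quarterly visits a year | 4 of 4 |
| EOS/ET | 1, at time of stopping | no stated row |

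Visit 11 has no vital signs. On the nominal schedule a switcher starts somatrogon around Week 52, has vital signs at Week 56 (56 − 52 = 4 weeks) and next at Week 65 (65 − 52 = 13 weeks). The first tabulated post-switch value is therefore at about 13 weeks.

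**Step 2: planned outputs side by side.**

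| Output | Protocol 8.6.9 | SAP 6.5.3 |
|---|---|---|
| Visits | every scheduled visit | baseline and Months 3, 6, 9, 12 |
| Absolute value and raw change | yes | yes |
| Percent change | not mentioned | yes |
| Abnormal results by visit | yes | not stated |
| Age-, sex- or height-standardised score | not mentioned | not stated |

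**Step 3: how far ageing alone could move the mean.** The documents give no drift rate. Assume that systolic pressure rises by d = 0.5 to 2 mmHg a year with no drug effect, from about 95 mmHg. With t years since baseline, mean change = d × t and percent change = 100 × d × t / 95. At the end of OLE Year k, t = k + 1 from the main-study baseline and t = k from an OLE baseline.

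| End of | From main-study baseline | From OLE baseline |
|---|---|---|
| OLE Year 1 | t = 2: 1.0 to 4.0 mmHg (1.1 to 4.2%) | t = 1: 0.5 to 2.0 mmHg (0.5 to 2.1%) |
| OLE Year 3 | t = 4: 2.0 to 8.0 mmHg (2.1 to 8.4%) | t = 3: 1.5 to 6.0 mmHg (1.6 to 6.3%) |
| OLE Year 4 | t = 5: 2.5 to 10 mmHg (2.6 to 10.5%) | t = 4: 2.0 to 8.0 mmHg (2.1 to 8.4%) |

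For heart rate, assume a fall of 2 to 4 beats/min a year. At OLE Year 3 the mean change is −8 to −16 beats/min (4 × 2 to 4 × 4) from the main-study baseline, or −6 to −12 (3 × 2 to 3 × 4) from an OLE baseline.

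Percent change rescales the drift without removing it. The choice of baseline alone moves the systolic figure by one year of drift, 0.5 to 2 mmHg.

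**The case against.** The case for leaving SAP 6.5.3 as it is has real substance.

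- **No reading is lost.** All values are listed, and clinically significant findings enter the AE tables. This stands, and it limits the harm. But listings and investigator-judged events do not show a shift in the group mean or the share of children outside limits for their age.
- **The SAP may depart from the protocol.** SAP section 2 says so, and protocol 8.6.9 itself asks for raw change. Both are true, so reporting raw change is not an error. The narrower visit list is permitted, but no reason is given for it.
- **Protocol 8.6.9 may have been written for the main study.** The LT-OLE paragraph of protocol 8.6.6 asks only for summaries by year and overall. However, 8.6.9 carries no such restriction.
- **The single-arm design limits every extension endpoint.** This is a design feature, not a fault of 6.5.3, and a reference score would not replace a control. It would reduce the age component, as the SAP already does for height.
- **Other tables may exist.** SAP 6.5 defers to the sponsor's safety rulebook, which is not available here, and the table list in SAP Appendix 6 is redacted. A categorical vital-sign table cannot be ruled out. If there is one, that part of the point falls away.

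A reader might go further and infer that vital signs are reported purely as change, that the Visit 12 and EOS/ET readings are discarded, or that they are the most informative ones. The documents do not support this. Absolute values are tabulated, every reading is listed, and nothing in either document says that vital-sign effects peak at one month or at termination.

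**Conclusion.** The point holds as a reporting gap in a descriptive safety endpoint. As written, SAP 6.5.3 covers fewer visits than protocol 8.6.9 and states no abnormal-results table. It leaves the vital-sign baseline open, and its statistics cannot separate ageing from drug effect over several uncontrolled years.

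The coverage loss is small and specific: one of five first-year visits, for switchers only, and none at the quarterly visits from Year 2. The absence of EOS/ET readings from the tables is inferred from the word *only*. The SAP does not say whether a termination reading near a quarterly time point would be assigned to it.

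The drift sizes rest entirely on the assumed annual rates and, for percentages, on the assumed 95 mmHg starting level. They show why the baseline and the scale matter; they do not predict the data. A reader might also be tempted to express the drift as a multiple of its standard error. That would need an SD of change and a number of children remaining at OLE Year 3, neither of which the documents give, and SAP 5.1 plans no hypothesis test against which to judge it.

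The primary height-velocity analysis is untouched. The change is worth making because it is cheap and uses data already scheduled for collection.

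**What to change.** Amend SAP 6.5.3 as follows.

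1. Add Visit 12 (switchers) and a last-reading or EOS/ET row to the tabulated time points, and restore the abnormal-results table of protocol 8.6.9. First-year coverage for switchers then becomes 5 of 5. If the sponsor prefers the shorter list, give the reason for departing from the protocol.
2. State whether the vital-sign baseline is the main-study or the OLE baseline.
3. Keep absolute values and raw change, and beside them give systolic and diastolic pressure as SDS or percentile for age, sex and height, and heart rate as SDS or percentile for age, from one named paediatric reference. Report n (%) outside that reference's age-specific limits by OLE year.

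The cost is SAP wording, some programming and the naming of one external reference. No new data are needed: age and sex are known and height is measured at the quarterly and EOS/ET visits. Visit 12 has no height measurement, so the nearest height would be used there. The change concerns tabulation alone and alters no clinical rule.

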6.5.4. Physical Examination

Physical examination and neurologic assessment data will be listed only by participant and visit.

7. INTERIM ANALYSES

There is no planned interim analysis in this study.

9. APPENDICES

Appendix 1. Summary of Efficacy Analyses

Not applicable.

Appendix 2. Data Derivation Details

Appendix 2.1. Definition and Use of Visit Windows in Reporting

Annual ADA characterization will be performed based on the algorithm below using visit windows as applied to ADPC dataset.

Period	From	To
Main	Day 2 (main dosing +1)	Day 410
OLE Year 1	Day 2/OLE Baseline (OLE dosing +1)	Day 410 (OLE Month 12)
OLE Year 2	Day 411	Day 774
OLE Year 3	Day 775	Day 1138
OLE Year 4	Day 1139	Day 1502

The following table will provide the adverse events reporting period to a given study period.

Period	From	To	AE linking to study period
Main	On or post first Main dosing date/time (in exposure dataset)	Prior to the first OLE dosing date/time	If the new AE strictly starts between the start and end dates of a given period, it will be counted in that period.
OLE Year 1 (visit13 -16)	On or post first OLE dosing date/time (defined in exposure dataset)	Visit 16 end date; if Visit 16 is missing, then first OLE dosing date + 365	
OLE Year 2 (visit 17-20)	“OLE Year 1 To” date + 1	Visit 20 end date; if Visit 20 is missing, then “OLE Year 2 From” date + 365	
OLE Year 3 (visit 21-24)	“OLE Year 2 To” date + 1	Visit 24 end date; if Visit 24 is missing, then “OLE Year 3 From” date + 365	
OLE Year 4 (visit 25-28)	“OLE Year 3 To” date + 1	Visit 28 end date; if Visit 28 is missing, then “OLE Year 4 From” date + 365	

Appendix 2.2. Endpoint Derivations

Not applicable.

Appendix 2.3. Definition of Protocol Deviations That Relate to Statistical Analyses/Populations

Not applicable.

Appendix 3. Data Set Descriptions

Not applicable.

Appendix 4. Statistical Methodology Details

Not applicable.

Appendix 5. List of Abbreviations

Abbreviation	Term
ADA	Anti-drug antibody
AE	Adverse event
AESI	Adverse event of special interest
AHV	Annualized height velocity
BA	Bone age
BM	Bone maturation
CA	Chronological age
CDISC	Clinical Data Interchange Standards Consortium
CDC	Center of Disease Control and Prevention
CS	Clinical significance
CTP	C-terminal peptide
DSMB	Data Safety Monitoring Board
FAS	Full analysis set
FSH	Follicle-stimulating hormone
GHD	Growth hormone deficiency
hGH	Human growth hormone
HT	Height
HV	Height velocity
IGFBP3	Insulin-like growth factor-binding protein-3
IM	Intramuscular
INN	International Nonproprietary Name
LH	Luteinizing hormone
LT-OLE	Long-term open-label extension
MedDRA	Medical Dictionary for Regulatory Activities
OLE	Open-label extension
MedDRA	Medical Dictionary for Regulatory Activities
PP	Per protocol set
PT	Preferred term
r-hGH	Recombinant human growth hormone

Abbreviation	Term
SAE	Serious adverse event
SAP	Statistical analysis plan
SC	Subcutaneous
SD	Standard deviation
SDS	Standard deviation score
SOC	System organ class
TEAE	Treatment-emergent adverse event

